## 12.0 Data Management

Audio-recordings and transcripts will be stored on a secured MUSC server. Demographic and clinical data will be entered into REDCap and analyzed using the Statistical Package for the Social Sciences (SPSS). All hardcopy documents (consent forms and data collection instruments) will be stored in a locked cabinet inside a locked office at the College of Nursing. Access will be limited to authorized study personnel.

### Protecting Confidentiality of Participant Data:

*Certificate of Confidentiality.* This study will be conducted in accordance with recently enacted policy regarding the automatic granting of Certificates of Confidentiality to NIH/NINR federally funded research. Participants will be made aware of their rights and the limitations of the release of Protected Health Information during the Informed

Consent process.

***Participant Screening and Enrollment.*** All data from participants screened for the study will be entered into an electronic study database. Designated research staff will collect, gather, and enter required data (written informed consent, documented assent for youth participating, HIPAA Authorization, and demographics) onto study data forms. Screened patients who do not meet study eligibility will have specific screening data entered into the study database. The collected data will be helpful in examining the patient population and feasibility of enrollment criteria and will include reason for exclusion. All dates will be shifted and other Personal Health Information (PHI) will be removed from the study database upon study completion. All data obtained from this study will be used for research purposes only and will comply with Federal HIPAA regulations. Master Screening and Enrollment Logs will be used by the PM to prepare reports on accrual and attrition for the PI and SMC.

***Case Report Forms (CRF).*** All proposed study specific case report forms (source documents) for data collection will be designed by the PI, and, when possible, transferred into electronic Case Report Forms (eCRFs) for use in the study's REDCap database. These study specific eCRFs source documents (study logs for correspondence, compensation and other forms such as pre-eligibility screens) will be coded by the participant's unique study ID# for all data collected including study instruments will be maintained in the participant research record. Completed instruments that require signature on a paper CRF will be scanned and uploaded into the study database to all for remote electronic safety monitoring as well as maintained on file in accordance with MUSC policies and applicable Federal Regulations for the Conduct of Human Participant Research.

***Binders.*** The PC will prepare and maintain a participant-specific CRF binder for each participant containing all non-eCRFs records. A regulatory file will be maintained by the PM to include the IRB-approved Protocol, original Informed Consent documents, HIPAA forms and other required study-related regulatory documents. All paper research records and CRFs will be maintained in a locked file cabinet, stored in a room for research files that is accessible only via a password protected entry system that features security cameras, within the College of Nursing. Access to the research records, study database and PHI will be restricted to authorized study personnel as approved by the PI and MUSC IRB. As with all studies conducted at MUSC, this study is also eligible for a random audit by MUSC Office of Compliance.

***Data Processing.*** This study will use Research Electronic Data Capture (REDCap) for data capture and management. REDCap is a software toolset and workflow methodology for the electronic collection and management of research and clinical trials data. REDCap provides secure, web-based, flexible applications, including real-time validation rules with automated data type and range checks at the time of data entry. Exports are made available for several statistical packages including SPSS, SAS, SUDA, R and Microsoft Excel. The study-specific REDCap electronic database will be designed and developed by the PI, CI, or PC. The provision of REDCap is made available through the South Carolina Clinical & Translational Research (SCTR) Institute at MUSC with NIH Grant awards UL1RR029882 and UL1TR000062. This study will also use Doxy.me, a secure video conferencing platform that is HIPAA compliant and freely available to MUSC researchers through SCTR.

***Data Security.*** Ensuring data security, compliance with 45 CFR 46 and maintaining the integrity of PHI is a top priority. MUSC has Standard Operating Procedures (SOP) to ensure a high level of data security while coordinating electronic and paper data management activities for clinical research trials. The REDCap study database will be hosted in the Biomedical Informatics secure data center at MUSC, a secure environment for data systems and servers on campus, and includes firewall, redundancy, failover capability, backups and extensive security checks. The secure data center has strict access control; only authorized core personnel may access the facility un-escorted. Only authorized users are allowed to connect to the network, and the security of the network is actively monitored. Power and environmental controls have several layers of backups, from interruptible power supplies to alternate and redundant feeds to the local utility company. The REDCap system administrator contributes to the maintenance of institutional disaster recovery and business continuity plans. Load balancers and a highly fault tolerant SAN infrastructure contribute to high availability.

The REDCap system itself has several additional layers of protection including password protection. Access to the data and its security is managed institutionally by sponsored login IDs through a Shibboleth login with an MUSC

issued NetID and features a user account management filter that controls who can access the data and to what degree. All personnel must pass an employment background check before being issued an ID. Password complexity, history and expiration standards are implemented at the institutional level. Access to individual REDCap projects and their data is managed by the owner of the project. All transactions are securely delivered to the application using Secure Sockets Layer (SSL – SHA-1 with RSA Encryption; 2048-bits). It is then transmitted internally (behind the firewall) to the database server. All transactions are logged at the server layer (httpd logging), application layers (REDCap logs activity to a database table), and the database layer, using both query and binary logging. This feature provides audit trails for all changes, queries, data exports and reports. MUSC Information security policies are available at: <https://mainweb-v.musc.edu/security/policy/>

*Data Entry.* Only MUSC IRB approved study personnel that are authorized to have access to the REDCap study database will be granted password access. Study personnel using computers that are connected to the Internet will directly enter data into the remotely housed database. As such, no electronic study data will be stored on hard drives and/or any portable electronic devices. Additionally, all personnel with access to the database will have current University of Miami CITI training in the Conduct of Human Subject Protections, and HIPAA and Information Security trainings that are completed annually. Each participant will be assigned a unique study identifier, all PHIs will be masked, and data exports will be limited to the PI or the PC for generating reports and the conduct of statistical data analysis.

*Data Monitoring.* Ongoing quality control procedures will be implemented for data collection, storage and processing. The PM will conduct routine monitoring of the study database and generate a monthly report for review at study team meetings. Standing agenda items for these meetings will include participant recruitment and retention, AE's, protocol deviations, data integrity and overall study conduct. The PI and PC will work to resolve and validate discrepant data. Discrepancies that warrant clarification will be sent to appropriate parties for review and resolution. All data entry and changes made in the study database by authorized study personnel will be automatically logged by REDCap, which will provide a transparent visible audit trail for reviewers.

### **13.0 Provisions to Monitor the Data to Ensure the Safety of Subjects (if applicable)**

We have a well-developed and NIH/NINR prepared Data Safety Monitoring Plan (DSMP) that involves the use of a Safety Monitoring Committee (SMC) that shall meet semi-annually following study initiation (i.e., recruitment of first participant). The Committee is comprised of key individuals that include: an independent safety monitor (ISM), a biostatistician (BS), and the Program Manager (PM). All reports will be forwarded to the IRB and Sponsor in accordance with institutional policies and sponsor requirements.

**[name] PhD, Biostatistician (BS).** [name] is a Professor in the College of Nursing with a joint appointment in the Department of Biostatistics, Bioinformatics and Epidemiology (DBBE) at MUSC. [name] has served and is currently serving as a member of several NIH/NINR R01/R21 DSM Boards, and Committees. [name] will be responsible for conducting semi-annual interim analyses, generating semi-annual AE safety reports from the electronic study research database and disseminating de-identified information to the ISM and other members of the SMC. The interim data analyses will only include safety related results; analyses in regard to study outcome will not be performed. The interim AE reports will provide typology, frequency data and outcomes of all reported and documented AE in the electronic study database. With no patient contact, [name] has no apparent conflict of interests to serve in this capacity.

**[name] MSc, Program Manager (PM).** [name] is the P20 Program Manager at the College of Nursing and a member of MUSC Institute of Human Values with Fellowship certification in Research Ethics. [name] has served and is currently serving as a member of several NIH/NINR R01/R21 DSM Boards and Committees, and FDA Industry Sponsored Clinical Trials. With no patient contact, [name] has no apparent conflict of interests to serve in this capacity. [name] will be responsible for the classification of all reported adverse events (AE) and for ensuring that all serious adverse events (SAE) are forwarded to the PI and ISM in real time and in compliance with MUSC IRB policies and procedures. In addition, and in conjunction with the PI, [name] will be responsible for amending the protocol in accordance with the ISM recommendations, submitting reportable SAEs and protocol deviations to MUSC IRB, and, submitting annual Progress Reports to the NIH/NINR through MUSC's OSRP. He will also be responsible for maintaining the regulatory binder, ensuring data management validation and verification of the electronic study research database, conducting monthly internal quality control audits on all participant records, notifying the PI of any deficiencies, and the forwarding of reportable SAE to the NIH/NINR Program Official through MUSC's OSRP within 72hrs of IRB review and acknowledgement

## Monitoring Study Safety

Good Clinical Practices (GCP) will be followed throughout this study. From the initial screening of participants through review of inclusion and exclusion criteria to the informed consent process to the provision of participant study instruction to staff training in Good Clinical Practices (GCP) and regulations pertaining to the Conduct of Human Participant Research to study contact with participants to internal monthly quality control audits and protocol fidelity monitoring to the real-time review of Adverse Events (AEs) and SAEs by the SM to the oversight of MUSC's IRB, procedures for monitoring study safety are consistently afforded throughout study. Specific study safety procedures include:

- Participants will be screened for inclusion and exclusion per the protocol; the PI or Research Coordinator (RC) shall verify potential participant eligibility prior to study enrollment.
- Participants will be fully informed as to all known risks and the possibility of risk from study participation during the informed consent process. Youth interested in participating will be asked to provide documented written assent, along with parental consent prior to enrollment. All adult participants will provide written informed consent prior to participating in any study procedures. Study risks will be provided in writing to participants via the informed consent document and will be reviewed verbally as part of the informed consent procedures. Participants will have the opportunity to ask questions prior to making a decision regarding whether they wish to volunteer for this research study. Study risks are minimal.
- Participants will be instructed to notify the researchers of any/all suspected or experienced adverse events whether they believe them to be related or not to the intervention.
- All reported participant AEs will be tracked through to resolution and reported to the IRB and Sponsor, as required per GCP and regulatory requirements.

- All investigators and researchers will maintain active CITI Human Subject Research and Good Clinical Practice training.
- The PM will conduct a monthly internal quality control audit of all participant records to ensure compliance with MUSC IRB regulations; the PI and Program Coordinator (PC) will work together to correct any errors.
- The PI and/or designee will observe and evaluate ten (10%) percent of eligibility screening visits, informed consents and study instructions performed by IRB approved study personnel and provide feedback and/or retraining of study personnel if fidelity to both applicable federal regulations and the protocol is not observed.
- The BS will generate semi-annual AE reports for the PI and SMC to review.
- The SM will have access to real-time study data and will be able to provide immediate recommendations to the PI.
- Investigator performance and compliance will be provided for through MUSC IRB and ORI study oversight.
- This protocol will be conducted fully in keeping with the signed MUSC IRB Principal Investigator Statement of Assurance and Department Chair's Statement of Assurance, when submitted to the IRB as a required component of the MUSC IRB Human Research Review Application. Diligent study safety monitoring will be conducted by all member of the research team and the SMC throughout the conduct of this study in compliance with the following required elements of MUSC IRB's continuing review process:
- Tracking and follow-up of participant accrual (including withdrawn consents) will minimize risk by identifying, disclosing, and mitigating any potentially unknown risk(s) of harm to study participants.
- Timely and appropriate reporting of informed consent process deficiencies, protocol deviations, privacy breaches, conflicts of interest, and/or changes in personnel.
- Ongoing soliciting, monitoring and appropriate reporting of adverse event activities.
- Timely and appropriate IRB submission of safety-related documents such as audit reports, sponsor progress reports, SM reports, and other materials or communications that might impact the safe conduct of this study.
- Active cooperation with the IRB, ACO, sponsor, and other applicable entities in the event of a random or for-cause internal or external audit.

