## 3.0 Intervention to be studied

MATADORS is a multi-component self-management intervention for youth with asthma and obesity that will be delivered via mobile device over a 4-week period and will include tailored content based on the existing SAMS (medication inhaler adherence for children with high-risk asthma) and SELFY (family-centered symptom self-management for children with sickle cell disease) mobile health applications and participation input from Phase I of this study. Participants randomized to the control arm (n = 15) will be enrolled in the existing SAMS symptom tracking and EMA assessment program to include baseline assessment, EMA symptom reporting, and repeated measures at 4 & 8 weeks. Participants randomized to the intervention arm (n = 15) will have continuous access to educational content within the app and weekly nurse-guided support available through videoconferencing support and text messaging to promote engagement. Intervention procedures will include symptom monitoring through self-report and completion of measures (Table 1), accessing of educational content, engagement with study team to increase engagement, use of activity trackers, and photo/voice/video diary entries completed through the app. At study completion, youth and their primary caregivers from both the intervention and control groups will complete an end of study interview.

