## 7.0 Setting

Study procedures will take place using virtually using communication means such as telephone, email or meeting platforms, such as Microsoft Teams or DoxyMe. In-person informed consent may be collected in a private MUSC clinic or office space, pending participant preference and current social distancing requirements. As an alternative to in-person consent, participants will be offered the option to provide e-consent via the MUSC e-consent REDCap template or DoxyMe. Initial study procedures (consent, basic demographic and baseline measures, and study instructions) and measure completion at 4-week intervention and 8-week follow-up will be completed remotely using REDCap. Post-exit interviews will be conducted via Microsoft Teams or DoxyMe.

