## 10.0 Study Design / Methods

This feasibility study is an 8-week, longitudinal randomized controlled trial (RCT) with 3 study visits (baseline, week-4, and week-8) among youth 10-17 years old (n=30) with asthma and >85% BMI and their primary caregivers (n=30). Eligible participants that agree to consent, will be randomized 1:1 into the MATADORS intervention or control group. Randomization will be performed by the study coordinator in REDCap utilizing a

scheme generated by the study biostatistician. The PI will be blinded to study allocation until the end of study follow-up interview. Participants randomized to the control arm (n = 15) will be enrolled in the existing SAMS symptom tracking and EMA assessment program to include baseline assessment, EMA symptom reporting, and repeated measures at 4 & 8 weeks. Intervention participants (n = 15) will have continuous access to educational content within the app and weekly nurse-guided support available through videoconferencing support and text messaging to promote engagement. Intervention procedures will include symptom monitoring through self-report and completion of measures (Table 1), accessing of educational content, engagement with study team to increase intervention engagement, use of activity trackers, and photo/voice/video diary entries completed through the app. During engagement with study team, participants will receive feedback on the one-time video inhaler technique submitted via the MATADORS app. At study completion, youth and primary caregivers will complete an end of study interview. Interviews will be audio-recorded and professionally transcribed.

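### Adverse-event capture is not standardised across arms that have unequal staff contact, so control events may be under-captured and any by-arm count may be biased

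*Combined protocol and SAP*

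**What the plan says.** **Detection.** Section 13.0, under Monitoring Study Safety, states: "Participants will be instructed to notify the researchers of any/all suspected or experienced adverse events". This applies whatever they think the cause was. Further down, a list of elements of the IRB's continuing review includes "Ongoing soliciting, monitoring and appropriate reporting of adverse event activities". No schedule, form or responsible role is attached to that soliciting, and nothing says it is the same in both arms. Table 1 contains no adverse-event item at any time point.

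**Contact.** Section 10.0 gives the intervention arm "weekly nurse-guided support available through videoconferencing support and text messaging to promote engagement"; section 3.0 sets the intervention at 4 weeks. Controls are assigned to an "existing SAMS symptom tracking and EMA assessment program to include baseline assessment, EMA symptom reporting, and repeated measures at 4 & 8 weeks". Section 7.0 adds that "measure completion at 4-week intervention and 8-week follow-up will be completed remotely using REDCap", so these time points need not involve a live conversation. Section 3.0 provides one later contact for everyone: "youth and their primary caregivers from both the intervention and control groups will complete an end of study interview".

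**Reporting channels.** The compensation paragraph in section 10.0 pays intervention youth as much as $4 a day for symptom and medication reports, tracker use and diaries. Controls are paid as much as $1 a day for symptom reports and tracker use.

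**Output.** Section 13.0 describes the biostatistician's semi-annual reports: "The interim AE reports will provide typology, frequency data and outcomes of all reported and documented AE". Arm is not mentioned. Section 4.0 lists withdrawal due to an adverse event among the study endpoints.

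**The concern.** When events are counted mainly because someone mentions them, the count depends on how often there is an occasion to mention them. Here those occasions differ by randomised arm. A nurse in weekly contact with a family is likely to hear about events whether or not asking is part of the job, and diaries offer a further route. A control family has symptom prompts, remote forms and one interview.

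Two things are at stake. First, events in control youth may go unrecorded, which weakens oversight of half the sample and makes even a pooled frequency hard to interpret. Second, a reader who splits the counts by arm could see an excess in the intervention arm that reflects observation rather than harm. That reading is foreseeable: section 15.0 tells participants that side effects may differ between the arms, and section 17.0 says results will be published and posted.

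**Working it through.** The plan gives no adverse-event rate, detection probability or by-arm analysis, so there is no figure of its own to reproduce. The check has two parts.

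**1. Routes by which an event could reach staff, by arm**

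| Route | Intervention | Control |
|---|---|---|
| Instruction to notify staff (13.0) | yes | yes |
| Soliciting (13.0) | named, no procedure | named, no procedure |
| Symptom reporting (3.0, 10.0) | yes | yes |
| Week-4 and week-8 remote measures (7.0) | yes, no adverse-event item | yes, no adverse-event item |
| Exit interview (3.0) | yes | yes |
| Weekly nurse support (3.0, 10.0) | available | not described |
| Diaries (3.0, 10.0) | yes | not described |
| Maximum daily reporting pay (compensation paragraph) | $4 | $1 as stated |

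The control figure in the last row does not fit the paragraph's own total. The stated items sum to 30 + 2 × 25 + 25 + 10 + 30 × 1 = $145, against a stated maximum of $175. A maximum of $175 would need (175 − 115)/30 = $2 a day. The intervention total does agree: 115 + 30 × 4 = $235. At $1 or $2, the incentive still favours reporting in the intervention arm.

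**2. Illustration of size (all rates assumed)**

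Input from the documents: 15 youth per arm. Assumed: the same true proportion p with an event in both arms, and detection d(C) in controls and d(I) in the intervention arm.

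Expected recorded youth = 15 × p × d. The gap is 15 × p × (d(I) − d(C)).

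| p | d(C) | d(I) | Control | Intervention | Gap | P(intervention count > control count) |
|---|---|---|---|---|---|---|
| 10% | 0.7 | 0.9 | 1.05 | 1.35 | 0.30 | 0.44 |
| 30% | 0.7 | 0.9 | 3.15 | 4.05 | 0.90 | 0.57 |
| 30% | 0.5 | 0.8 | 2.25 | 3.60 | 1.35 | 0.65 |
| 30% | 0.5 | 0.9 | 2.25 | 4.05 | 1.80 | 0.72 |
| 50% | 0.5 | 0.9 | 3.75 | 6.75 | 3.00 | 0.84 |

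The last column comes from two independent exact binomials. With equal detection of 0.8 in both arms it is 0.36 to 0.43 over p from 10% to 50%, and the expected gap is 0. Over the full set of unequal pairs, the chance of a nominally significant difference at two-sided 0.05 is about 4% to 20%. That last range uses a normal approximation, which is rough at 15 per arm.

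The ratio of recorded counts is d(I)/d(C), because p cancels: 0.9/0.7 = 1.29 and 0.9/0.5 = 1.80. It only restates the assumed detection rates and is not evidence of size.

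The table also lets unequal detection run for all 8 weeks. If it applied only to the 4 intervention weeks and events were spread evenly, mean intervention detection would be (d(I) + d(C))/2 and each gap would halve: 0.30/2 = 0.15 to 3.00/2 = 1.5 youth.

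**The case against.** A reader might infer that adverse events rest on notification alone, that the nurse solicits events in one arm while the other must volunteer them, and that counts will therefore differ through ascertainment. The documents do not support that reading. Section 13.0 names soliciting and does not confine it to one arm. Nurse support is described as available and as serving engagement; nothing says the nurse asks about events or that every dyad is seen weekly. Both arms share the instruction to notify, symptom reporting, two sets of measures and an exit interview, and no arm difference in contact is described for weeks 5 to 8.

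Three further points have weight. No by-arm adverse-event table or test is stated, and section 4.0 reads as a list of ways participation can end. The protocol calls study risks minimal. Absence from Table 1 is not conclusive either, because that table covers feasibility and outcome measures. Section 13.0 refers to a prepared safety monitoring plan, and the case report forms are not reproduced in the text examined, so a query on those forms cannot be excluded.

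These points remove certainty about direction and size. They do not supply a procedure: as written, the soliciting cannot be carried out identically in both arms, because nothing says when, how or by whom it is done.

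**Conclusion.** The concern holds as a gap in standardisation. The only concrete step is participant notification, the soliciting has no schedule or form, and the intervention arm has extra nurse contact and reporting channels during the 4-week intervention. Control events may be under-captured, and adverse-event counts or related withdrawals read by arm may be biased upward in the intervention arm.

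The size is unknown. Under the assumed rates above, the expected gap is 0.3 to 3.0 youth, or about half that if the imbalance is confined to the intervention weeks. That is small in absolute terms, but every count will be small with 15 per arm, so one or two cases could change the impression. The bias in comparison arises only if counts are tabulated or interpreted by arm; weaker capture in control youth does not depend on that.

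**What to change.** - Add the same short adverse-event question to the existing week-4 and week-8 REDCap forms in both arms.
- For each event, record how it was found: scheduled question, spontaneous notice, nurse contact, symptom report or diary.
- If counts are shown by arm, present those from the scheduled question alongside the all-source counts, and say which is which.
- Continue to send events from every source to the Safety Monitoring Committee.

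This gives the soliciting already promised in section 13.0 a schedule and a form. The cost is one item at two existing time points, about a minute of participant time per visit, plus a source field on the adverse-event record. It does not remove the extra contact in the intervention arm, but it gives both arms one channel that is the same.
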